#### Open-Label Period (Treatment Cycles 2-4)

For a given subject, the Dysport dose for treatment cycles 2, 3 and 4 will be based on the investigator's judgement (based on efficacy and safety).

- Treatment cycle 2: the Dysport dose can either be the Dysport dose assessed in the previous treatment cycle (double-blind period) for the current cohort or the Dysport dose of the following cohort (provided it has been approved by the DRC).

- Treatment cycles 3 and 4: the Dysport dose can either be the dose assessed in the previous treatment cycle, a lower dose or the dose of the following cohort (provided it has been approved by the DRC).

If any subject fulfils the retreatment criteria and needs a higher dose for treatment prior to the DRC having approved the next dose level, the subject can either accept the dose level currently on, or delay injection until the next dose level is approved by the DRC or withdraw from the study.

A subject can receive up to a maximum of 4 treatment cycles with Dysport. The last treatment cycle should last at least 12 weeks and should not be initiated after Week 36.

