### 3.7.3 *Retreatment Criteria (Stage 1 and Stage 2)*

From Week 12 onwards (Stages 1 and 2), need for retreatment will be assessed at each visit. All subjects willing to continue in the study will be offered to receive Dysport (under an open-label design).

Retreatment with Dysport will only be initiated if all of the following criteria are fulfilled (retreatment criteria):

- At least 12 weeks have elapsed since the last treatment received.
- Based on investigator's judgement, this is in the best interest of the subject.
- Subject is willing to be retreated.
- The subject has not experienced any unacceptable AE as judged by the investigator.
- Negative urine pregnancy test.
- Negative drug screen test for illicit drugs.

Details on dose administration for Stage 1 are provided in Sections [3.7.2.1](#) and for Stage 2 in Section [3.7.2.2](#).

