- a From Week 12 onwards, if no retreatment is required, the subject will attend Additional Visits every 6 weeks until retreatment is required or Week 36 (EOS) is reached. When subject is eligible and all retreatment criteria are fulfilled at any visit, the subject will complete all the assessments planned at this visit, all assessments planned at End of Cycle 1 (if not already performed at the visit) and will enter Cycle 2 Day 1 (which will be on the same day as End of Cycle 1).
- b This visit (Week 36) is the End of Study if the subject is still not eligible for retreatment at the End of Cycle 1.
- c ICF to be signed prior to any screening assessment.
- d To be performed only if this visit is the End of Study or Early Withdrawal.
- e To be assessed at Screening Visit, then 1 week prior to the next planned visit and at the visit. PGI-C will be assessed Week 6 onwards only.
- f To be assessed at the site during the visit.
- g To be assessed at Screening Visit, then 2 weeks prior and 1 week prior to the next planned visit and at the visit.
- h To be assessed at Screening Visit, and then from 2 weeks prior to the next planned visit, subjects need to record daily if they had intercourse, the number of intercourse instances, corresponding pain during each intercourse instance on an 11-point NRS, and details of pain rescue medication if taken to prevent or treat vestibular pain.

Study Procedures and Assessments	Pretreatment		Double-Blind Treatment Period Cycle 1							End of Cycle 1/ EOS or EWD [b]	
	V1	V2	V3	V4	V5 [a]	Additional Visits [a]					
						V6	V7	V8			
Visit Day/Week No.	Screening (Day -14) [m]	Baseline (Day 1)	Week 2 (Day 15)	Week 6 (Day 43)	Week 12 (Day 85)	Week 18 (Day 127)	Week 24 (Day 169)	Week 30 (Day 211)	Week 36 (Day 253)		
Type of visit	Clinic	Clinic	Telephone	Clinic	Clinic	Clinic	Clinic	Clinic	Clinic		
Visit Window	-14 days/ +3 days			±3 days	±5 days	+14 days	±14 days	±14 days	±14 days	±14 days	

i FSH only at Screening Visit.

j Performed after all the other procedures and assessments. Subjects to remain at the clinic for at least 30 minutes after the study drug administration.

k To be assessed weekly from 2 weeks prior to the next planned visit (assessment on the day of the visit should be avoided). Subjects need to rate the level of the corresponding pain following insertion of vaginal dilator (number 6 size) on an 11-point NRS and record details of associated pain medication if consumed.

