- a Day 1 should be done on the same day as last visit of previous cycle. During Stage 1, Day 1 can be delayed until the DRC has confirmed the dose for the next cohort.
- b From Week 12 onwards, if no retreatment is required, the subject will attend Additional Visits every 6 weeks until retreatment is required, or EOS is reached. When subject is eligible and all retreatment criteria all are fulfilled at any visit, the subject will complete the assessments planned at this visit and will enter Day 1 of the next Cycle on the same day and once the DRC has confirmed moving to next cohort for Stage 1.
- c Not to be performed if already done on the same day. AEs are assessed on a continual basis from signing of the ICF.
- d To be performed only if Day 1 is not on the same day as the last visit of previous cycle and the assessment was performed more than 2 weeks prior to Day 1.
- e To be assessed 2 weeks prior and 1 week prior to the next planned visit, and at the visit.

Study Procedures and Assessments	Open-Label Treatment Period Cycles 2 to 4						EOS / EWD
	V9, V13, V17	V10, V14, V18	V11, V15, V19	V12, V16, V20	Additional Visits [b]		
Visit Day/Week No.	Day 1 [a]	Week 2 (Day 15)	Week 6 (Day 43)	Week 12 [b] (Day 85)	Week 18 (Day 127)	Week 24 (Day 169)	Week 48 from Cycle 1 Day 1 (Day 337 from Cycle 1 Day 1) or Early withdrawal
Type of visit	Clinic	Telephone	Clinic	Clinic	Clinic	Clinic	Clinic
Visit Window		±3 days	±5 days	+14 days	±14 days	±14 days	±14 days

f To be recorded daily from 2 weeks prior to the next planned visit. Subjects need to record daily if they had intercourse, the number of intercourse instances, corresponding pain during each intercourse instance on an 11-point NRS and details of pain rescue medication if taken to prevent or treat vestibular pain.

g Performed after all the other procedures and assessments. Subjects to remain at the clinic for at least 30 minutes after the study drug administration.

h No assessment for retreatment if the visit occurs >36 weeks from Cycle 1 Day 1.

i To be assessed only in Cycle 2 (i.e. the first cycle of the open-label treatment period).

j To be assessed 1 week prior to the next planned visit and at the visit.

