#### 5.2.2.4 Week 12 Visit (Day 85 +14 days)

The following procedures will be performed:

- mFSFI (pain to be recorded 1 week prior to the visit and at the visit; other domains to be recorded only at the visit)\*
- Relationship/partner status (to be recorded weekly from 2 weeks prior to the visit and at the visit)\*
- mVPAQ (pain and life interference to be recorded 1 week prior to the visit and at the visit; other subscales to be recorded only at the visit)\*
- PHQ-9\*
- SF-36\*
- PGI-S (to be recorded 1 week prior to the visit and at the visit)\*
- PGI-C (to be recorded 1 week prior to the visit and at the visit)\*
- Intercourse details (to be recorded daily from 2 weeks prior to the visit)\*
- Dilator size 6 insertion details (to be recorded weekly from 2 weeks preceding the visit; assessment on the day of the visit should be avoided)\*
- Blood sampling (nonfasting) for haematology and biochemistry\*\*
- Dilator test
- Measurement of pelvic floor muscle pressure (in all subjects in Stage 1 up to 400 U and in a subset of subjects in Stage 2 (i.e. in subjects who have never had a vaginal delivery (included attempted vaginal delivery), and at study sites that were provided a perineometer to assess pelvic floor muscle pressure))
- CGI

- Review of AEs\*
- New or changed concomitant medications/nondrug therapies\*.

\*\*In the event of a remote visit being required, blood sampling should be performed as soon as onsite visit resume and prior to the Week 18 Visit (as much as possible) and recorded as an unscheduled visit.

Once these procedures have been performed, the need for retreatment will be assessed as described in Section 3.7.3:

- Subjects eligible for retreatment will complete the remaining End of Cycle 1 assessments and enter the treatment cycle 2 (open-label, see Section 5.2.3.1) on the same day or once the DRC has confirmed the dose of the next cohort;
- Subjects not eligible for retreatment will perform an Additional Visit 6 weeks later (see Section 5.2.2.5).

In the event of a remote visit being required, subjects should not receive re-treatment with Dysport until onsite visits resume.

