3.9 Safety

For the DB period, summary tables by DB treatment group will be provided on the Safety population.

For the Active Treatment Cycle, summary tables by number of active treatment cycles will be provided on the Active Treatment population. Additionally, a summary table will be also provided by dose received at each active treatment cycle on the Active Treatment population.

The summary tables will follow the strategy specified in Section 3.1.

3.9.1 *Extent of exposure*

To describe the duration of exposure, three durations of exposure will be calculated.

- Duration of study treatment exposure will be defined in weeks as:
(The date of last visit attended – treatment cycle 1 injection date + 1) / 7.
- Duration of treatment cycle will be defined in days as:
For subjects who are retreated at the end of the cycle, the duration of treatment cycle is calculated as (date of retreatment) - (treatment injection date).
For subjects who are not retreated at the end of the cycle, the duration of treatment cycle is calculated as (last attended visit date of the treatment cycle) – (treatment injection date) + 1.
- Duration of Active Treatment exposure will be defined in weeks as:
(The date of last visit attended – first Dysport injection date + 1) / 7.

The following summary tables will be provided:

- Description of study treatment exposure by DB treatment group + overall subjects on the safety population for DB period and overall subjects for the whole active treatment periods.
Study treatment exposure will be described both as a quantitative and qualitative variable.

- Description of duration of treatment cycle, for each treatment cycle, dose received of each treatment cycle and overall subjects from the safety population.
- Description of duration of treatment cycle, by dose received at the cycle and all doses combined on the active treatment population.
Active Treatment exposure will be described both as a quantitative and qualitative variable for each period of exposure.
- A summary table with the total number of subjects who received 1, 2 or 3 active treatment cycles and the total number of subjects who received at least 1, 2 or 3 active treatment cycles, all doses combined on Active treatment population and by DB treatment group + overall subjects.

To describe the doses received, the following summary tables will be provided:

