3.15 COVID-19 impact

The e-CRF was amended in order to collect data related to COVID-19 impact. These will be summarized as described thereafter.

Disposition

To assess the impact of COVID-19 pandemic on the trial, the following summaries will be provided:

- Proportion of subjects impacted and withdrawn due to COVID-19 pandemic.
 - the reasons of discontinuation related to COVID-19 will be presented separately.
 - the number of subjects exposed as well as impacted or infected will also be presented.
- Number of subjects with visits impacted by COVID-19 with the corresponding reason.
 - the number of subjects per visit as well as the number of subjects with a missing visit per timepoint.
 - the number of visits impacted due to COVID-19 with the reasons will be presented to assess the impact of COVID-19.

Demographic and Baseline characteristics

Summary statistics will be provided for demographic and Baseline characteristics, by DB treatment group in subjects recruited (based on informed consent date) before and after (inclusive) the start of COVID-19 pandemic [i.e. 27-Jan-2020 based on date when the Public health emergency was declared by Health and Human Services] in order to identify a potential change in the general subject's characteristics.

Exposure

To assess the impact of COVID-19 pandemic on the trial, the time elapsed between injections will be described for injections done before and after the start of COVID-19 pandemic (27-Jan-2020), which will be presented by cycle and one subject will be counted once per cycle and period. Any cycle that ongoing on 27-Jan-2020 or after 27-Jan-2020 will be considered as cycle after the start of COVID-19 pandemic.

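### The before/after COVID-19 comparison of time between injections assigns cycles partly by their own length, so it tends to show a delay even where there is none (minor)

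*SAP*

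**What the plan says.** SAP section 3.15, under Exposure, announces that "the time elapsed between injections will be described for injections done before and after the start of COVID-19 pandemic (27-Jan-2020"), presented by cycle. It does not say which of the two injections bounding an interval is meant. The next sentence settles the allocation by cycle: "Any cycle that ongoing on 27-Jan-2020 or after 27-Jan-2020 will be considered as cycle after the start of COVID-19 pandemic".

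SAP section 3.9.1 defines where a retreated cycle ends: "the duration of treatment cycle is calculated as (date of retreatment) - (treatment injection date"). For a cycle that contributes an interval, the end is therefore the next injection.

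The protocol lets that interval vary for reasons unrelated to COVID-19:

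- Section 3.7.3 sets the minimum: "At least 12 weeks have elapsed since the last treatment received".
- A footnote to Table 2 in section 5.1 provides for later retreatment: "if no retreatment is required, the subject will attend Additional Visits every 6 weeks until retreatment is required or Week 36 (EOS) is reached".
- A footnote to Table 3 in the same section adds waiting time in Stage 1: "During Stage 1, Day 1 can be delayed until the DRC has confirmed the dose for the next cohort".
- Section 3.7.2.1 limits late starts: "The last treatment cycle should last at least 12 weeks and should not be initiated after Week 36".

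Section 5.2.2.4 describes the delay that the table ought to detect: "In the event of a remote visit being required, subjects should not receive re-treatment with Dysport until onsite visits resume".

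**The concern.** The quantity summarised is the interval length, and the same length helps to assign the group. Take a woman injected on 01-Aug-2019. Retreated at 12, 18 or 24 weeks (24-Oct-2019, 05-Dec-2019, 16-Jan-2020), her cycle counts as before. Retreated at 30 or 36 weeks (27-Feb-2020, 09-Apr-2020), it counts as after. Nothing but the length differs. Presenting the table by cycle does not remove this, because the sorting happens within each cycle.

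Long intervals caused by clinical need or by waiting for a DRC decision can therefore be filed as after and read as pandemic delay. A cycle with no further injection has no elapsed time and adds nothing to the table, so a retreatment cancelled because of COVID-19 is invisible there.

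What is at stake is the reading of one summary: whether the pandemic changed the spacing of injections.

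**Working it through.** The SAP gives no figure for this table, so there is nothing to reproduce. The check asks what the rule returns when there is **no** COVID-19 effect.

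**Inputs from the documents.** Cut-off 27-Jan-2020. Cycle 1 retreatment at 12, 18, 24, 30 or 36 weeks (Protocol 3.7.3 and Table 2). No cycle started after Week 36 (Protocol 3.7.2.1). DRC meeting on 16 October 2020 followed by early closure (SAP 1.3.5); that is 263 days, or 37.6 weeks, after the cut-off.

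**Assumptions, not in the documents.** Injections spread evenly from A weeks before to B = 40 weeks after the cut-off, with A = 60 or 42. Two spreads of the interval L over 12/18/24/30/36 weeks:

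- Spread 1: 0.50/0.20/0.15/0.10/0.05, giving E[L] = 18.0 and E[L²] = 378.
- Spread 2: 0.70/0.15/0.10/0.03/0.02, giving E[L] = 15.12 and E[L²] = 259.92.

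**Step 1: all intervals completed.** An interval of length L is before if it started between A and L weeks ahead of the cut-off, which has weight A − L. It is after with weight B + L. Hence

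- mean before = (A·E[L] − E[L²]) / (A − E[L])
- mean after = (B·E[L] + E[L²]) / (B + E[L])

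Spread 1, A = 60: before = (1080 − 378)/42 = 16.7; after = (720 + 378)/58 = 18.9. False delay 2.2 weeks.

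Spread 1, A = 42: before = (756 − 378)/24 = 15.75; after 18.9. False delay 3.2 weeks.

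Spread 2: before = (907.2 − 259.92)/44.88 = 14.4 or (635.04 − 259.92)/26.88 = 14.0; after = (604.8 + 259.92)/55.12 = 15.7. False delay 1.3 or 1.7 weeks.

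**Step 2: retreatment stops S weeks after the cut-off, S = 38 to 44 (assumed).** Only intervals completed by S are seen. Every L then has the same weight S in the after group, because starts run from −L to S − L. The after mean is therefore just E[L]. The false delay falls to 18.0 − 16.7 = 1.3 or 18.0 − 15.75 = 2.25 weeks for spread 1, and to 15.12 − 14.42 = 0.7 or 15.12 − 13.96 = 1.2 weeks for spread 2.

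**Step 3: closer to the trial.** Cohorts 1 to 6 (5 × 10 + 8 = 58 planned subjects) were simulated with the Week 36 limit, assumed cohort dates and three assumed Cycle 1 spreads.

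| Situation | After minus before, weeks |
|---|---|
| Cycle 1, no stop, two wider spreads (means about 20.5 and 25) | 2.3 to 3.0 |
| Cycle 1, no stop, retreatment only at 12 or 18 weeks | 0.3 to 0.4 |
| Cycle 2, no stop | 0.2 to 0.7 |
| Cycle 1, retreatment stops 31-Oct-2020, two main sets of cohort dates | 0.1 to 1.3 |
| Same stop, cohorts 3 and 4 recruited early | −0.1 to 0.8 |

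Cycle 2 is less affected because it starts no earlier than Week 12 and its successor no later than Week 36, so, visit windows aside, its interval cannot exceed 24 weeks. For Cycle 3 the limit is 36 − 24 = 12 weeks.

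**Step 4: would a split by a date fixed at injection suffice?** Group by whether Day 85 (start plus 12 weeks) falls before the cut-off. With all intervals completed, both groups have mean E[L]. With a stop at S, the before group is still complete, but the mean of completed intervals in the after group is ((S + 12)·E[L] − E[L²]) / (S + 12 − E[L]). Spread 1: (900 − 378)/32 = 16.3 at S = 38 and (1008 − 378)/38 = 16.6 at S = 44, a false shortening of 1.7 or 1.4 weeks. Spread 2: 14.2 or 14.4, a false shortening of 0.9 or 0.8 weeks. The same split with Kaplan-Meier estimation, censoring at S, returned the true mean to within 0.05 weeks in both groups in every scenario.

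**The case against.** The rule has a rationale. A cycle running on 27-Jan-2020 is one whose retreatment could still be held up by remote visits, and SAP section 5.1.3 says the date was chosen to capture any impact on all cohorts, open-label cycles included. That explains the intention. It does not stop the rule from selecting short intervals into the before group.

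A reader might infer that the table is bound to show a spurious delay. The documents do not support that. Recruitment dates and retreatment timing are not given, the larger figures need many Cycle 1 intervals well beyond 18 weeks, and an early stop of retreatment removes long late intervals and works in the opposite direction. A false delay is the expected direction, not a certain outcome. Two biases that may partly cancel still do not make the table interpretable.

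A reader might also infer that the women most affected are left out of the report. They are missing from this table only. SAP section 3.15 (Disposition) counts COVID-related withdrawals, affected visits and missed visits with reasons, and section 3.9.1 gives a duration for cycles not followed by retreatment. What is lacking is a link between those counts and the intervals.

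The objection that a start-date split of completed intervals would bring in a bias of its own is correct (Step 4). The remedy must therefore handle censoring.

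**Conclusion.** The concern holds in a limited form. The allocation rule makes group membership depend on the length being summarised, and presenting by cycle does not cure that. With no COVID-19 effect it tends to lengthen the after group: by about 1 to 3 weeks if all intervals are completed, by 0.3 to 0.4 weeks in Cycle 1 if retreatment is nearly always at 12 or 18 weeks, and by less than the wider-spread Cycle 1 figures in Cycle 2. It may fall to about zero if retreatment closed soon after the October 2020 decision. All these sizes rest on assumed recruitment dates, retreatment frequencies and stop dates; the mechanism does not.

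Severity is minor. SAP sections 3.1 and 3.1.2 confine the analysis to descriptive statistics without formal testing, and no safety or efficacy conclusion depends on this table.

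**What to change.** In SAP section 3.15 (Exposure), replace the allocation sentence and the summary:

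1. Group each cycle by a date fixed at its injection: its Day 85 falls before 27-Jan-2020, or on or after it.
2. For each cycle number, describe time to next injection by Kaplan-Meier in the two groups instead of averaging completed intervals only. Censor cycles with no further injection at the last attended visit or at the date retreatment closed.
3. Beside it, show the number of censored cycles per group and how many have a COVID-19 reason in the eCRF.

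The cost is one derived date and a Kaplan-Meier summary in place of simple means. A few cycles that fell due just before 27-Jan-2020 but were delayed past it will count as before, which slightly dilutes a true effect.

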4 COMPUTER SYSTEMS, SOFTWARE AND VALIDATION OF PROGRAMS

4.1 Software

All tables, listings and figures will be produced and statistical analysis performed using SAS version 9.4.

4.2 Validation programs

Medpace will provide a Validation Plan to Ipsen identifying the methods of validation.

Copies of the internal QC forms produced for the validation process and Medpace's sign-off forms will be provided to the sponsor to support the validation.

4.3 Restitution of the programs

All programs (including Macros and analysis datasets) producing the tables, listings and statistical output along with associated logs should be given to the sponsor when the tables, listings, figures and statistical analysis has been finalised.

5 CHANGES FROM PROTOCOL

5.1.1 *Schedule of assessments*

The descriptive analysis to evaluate/describe any possible centre effect in protocol (section 11.4.4) is removed due to the small sample size.

5.1.2 *Data Analyses Timepoints*

The intermediate and primary analyses will not be performed. All analyses related to Stage 2 will not be performed since the study was terminated before Stage 2 begins. Please refer to Section 1.3.5 for more details.

5.1.3 *COVID-19 Pandemic Start Date*

The date 27-Jan-2020, when public health emergency was declared by Health and Human Services in the US, is used instead of the date specified in the protocol (i.e., when first subject randomised in Cohort 6) in order to describe any possible impact of COVID-19 pandemic on subjects followed-up in all cohorts, including during the open-label cycles.

5.1.4 *Per Protocol (PP) population*

No Per Protocol population will be defined as it was planned for the analysis of Stage 2 and the study was terminated before Stage 2 begins. Stage 1 efficacy analyses consist in descriptive only on the mITT population.

7 APPENDICES

7.1 Appendix 1: List of PCSA criteria

PCSA for blood chemistry parameters:

Parameter	PCSA
ALT/SGPT	$\geq 3 \times \text{ULN U/L}$
AST/SGOT	$\geq 3 \times \text{ULN U/L}$
GGT	$\geq 3 \times \text{ULN U/L}$
ALP (Alkaline Phosphatase)	$\geq 1.5 \times \text{ULN U/L}$ or $\geq 3 \times \text{ULN U/L}$
Creatinine	$\geq 150 \mu\text{mol/L}$ (Adults)
Blood Urea Nitrogen	$> 10 \text{ mmol/L}$
Chloride	$\leq 90 \text{ mmol/L}$ $\geq 115 \text{ mmol/L}$
Calcium	$< 1.75 \text{ mmol/L}$ $> 3 \text{ mmol/L}$
Sodium	$< 130 \text{ mmol/L}$ $> 150 \text{ mmol/L}$
Potassium	$< 2.5 \text{ mmol/L}$ $> 6 \text{ mmol/L}$
Total cholesterol	$> 6.22 \text{ mmol/L}$
Triglycerides	$> 2.26 \text{ mmol/L}$
HbA1c	$> 8\%$
Albumin	$\leq 25 \text{ g/L}$
Direct bilirubin	$> 2 \text{ ULN } \mu\text{mol/L}$
Total bilirubin	$> 2 \text{ ULN } \mu\text{mol/L}$
Phosphate	$< 0.75 \text{ mmol/L}$ $> 1.8 \text{ mmol/L}$
Total protein	$< 40 \text{ g/L}$

PCSA for haematology parameters:

Parameter	PCSA
White blood cell	$\leq 2.8 \text{ } 10^9/\text{L}$ $\geq 16 \text{ } 10^9/\text{L}$
Red blood cell	$< 3 \text{ } 10^{12}/\text{L}$ $> 6 \text{ } 10^{12}/\text{L}$
Hematocrit	≤ 0.32 and 0.03 decrease from baseline L/L (female) ≤ 0.37 and 0.03 decrease from baseline L/L (male)
Lymphocytes	$< 0.3 \text{ } 10^9/\text{L}$ $> 11.0 \text{ } 10^9/\text{L}$
Neutrophils	$< 1 \text{ } 10^9/\text{L}$ $> 13 \text{ } 10^9/\text{L}$
Monocytes	$> 2.3 \text{ } 10^9/\text{L}$
Basophils	$> 10^9/\text{L}$
Eosinophils	$> 10^9/\text{L}$
Hemoglobin	$\leq 95 \text{ g/l}$ (female) $\leq 115 \text{ g/l}$ (male)
Platelet count	$< 75.1 \text{ } 10^9/\text{L}$ $\geq 700 \text{ } 10^9/\text{L}$
